**Prisoners Form** 

Other

x None of the above populations are included in the research study

### The following documents are currently attached to this item:

There are no documents attached for this item.

### Participant recruitment

Please describe the plan to equitably identify and recruit a diverse group of participants that is reflective of the population under study. If this is a multicenter protocol, the recruitment plan should describe the local (Penn) site's plan. Describe:how potential participants may be identified (review of medical records, Slicer Dicer, DAC reports including referrals from physician offices and clinics);who may approach potential participants;methods to achieve sample diversity and inclusiveness;what information may be presented to or discussed with them; andthe context and setting in which recruitment will happen.

Subjects will primarily be recruited from the University of Pennsylvania through the online participant study pool, SONA. Individuals will receive a link to a web-based form after signing up where they will give their consent to participate in the study. If participant recruitment through SONA is insufficient to meet our target sample size, we will additionally recruit other University students from the United States through class email lists, social media platforms (e.g., Facebook class groups), and flyers (with a scannable barcode and detablable pieces with contract information) around campus. No participants under the age of 18 will be enrolled.

### **Recruitment Materials**

Is the research team using any recruitment materials? These may include but are not limited to: phone call scripts, radio/video scripts, flyers/brochures, internet postings, email, letters to potential participants, letters to patient physicians, My Penn Medicine (MPM), other direct messaging, etc. For guidance regarding recruitment materials, please review the IRB's guidance on Participant Recruitment Materials online:https://irb.upenn.edu/recruitment

#### Use of Penn Media & Social Media Services

Will the recruitment plan propose to use any Penn media services (communications, marketing, etc.) for outreach via social media avenues (examples include: Facebook, Twitter, blogging, texting, etc.) or does the study team plan to directly use social media to recruit for the research? Yes

Please identify which method(s) of social media you will utilize, the content of the text to be used, and the method(s) for posting this information (i.e., using Penn supported communication services). When proposing the text to utilize, please be aware of any social media limitations (i.e., number of characters allowed in a tweet) and any appropriate confidentiality practices necessary to be compliant with posting research recruitment text.NOTE: Penn Medicine must utilize one of the centralized PM Facebook Pages:ClinicalResearch@Penn Facebook pagePenn Medicine Facebook page@PennCancer Facebook pageAll clinical research paid Facebook ads must be listed on Clinical Research @ Penn Facebook page,www.facebook.com/ClinicalTrialsAtPenn. Exceptions to the above must get approval from the Penn Medicine Social Media Committee: [contact].

Social Media Text: Facebook: Researchers at @UPenn are seeking college students studying at the University of Pennsylvania who have access to a smartphone capable of downloading the Neuroflow application to spend approximately 1 minute each day completing the daily check in for 28 days and a maximum of 15 minutes filling out a pre and post study qualtrics survey. This study aims to understand incentives that encourage engagement with a mental health app in order to promote mental wellness

among college students. For more information: Please contact [name], Research Assistant at the Penn Center for Mental Health, at [contact] [link to flyer] Twitter: @UPenn seeking college students with smartphone access to download Neuroflow app to help understand the role of incentives in user engagement/promote mental wellness. Interested? Contact [name], @Penn Center for Mental Health, [contact] [link to flyer] Flyers have been uploaded under the Recruitment Materials tab.

# The following documents are currently attached to this item:

Subject recruitment (neuroflow-flyervertical3.pptx)
Subject recruitment (neuroflow-flyerhorizontal3.pptx)

# Subject compensation\*

Will subjects be financially compensated for their participation?

# The following documents are currently attached to this item:

There are no documents attached for this item.

If there is subject compensation, provide the schedule for compensation per study visit or session and total amount for entire participation, either as text or separate document

There will be no financial compensation for participation in this study. For students enrolled at the University of Pennsylvania who registered through the SONA system, 4 credits will be awarded after the completion of the study and prior to the end of the semester. Additionally, participants will not be compensated for enrollment in the study but if randomized to the controlled group they will be able to cash in accrued points received for completing app activities for gift cards(maximum points = 1000 per month =  $\sim$ \$10).

# **Study Procedures**

#### Suicidal Ideation and Behavior

Does this research qualify as a clinical investigation that will utilize a test article (ie- drug or biological) which may carry a potential for central nervous system (CNS) effect(s)? Centeral nervous system(CNS) effect: the ability of a test article to enter into and potentially interact with the central nervoous system (brain and spinal cord). Clinical Investigation: Any experiment that involves a test article and one or more human subjects that either is subject to requirements for prior submission to the Food and Drug Adminstration (FDA) under section 505(i) or 520(g) of the Federal Food, Drug, and Cosmetic Act, or is not subject to the requirements for prior submission to the FDA under these sections of the act, but, the results of which are intended to be submitted later to, or held for inspection by, the FDA as part of an application for a research or marketing permit.

#### **Procedures**

This study is a two-arm pilot randomized controlled trial to assess differences in user retention and usage rates associated with two incentive structures within the NeuroFlow app (I.e., general structure versus financial compensation). We will assess user engagement with utilization data (ie., daily, weekly, and monthly active users) and measures of the total number of activity counts completed by a user. After consenting to participate in the study, participants will be randomly assigned to use Neuroflow either with points only or with points and the opportunity to exchange those points for gift cards. In both conditions, participants will begin by completing a consent form and a brief questionnaire with their contact information, which will be used to grant them access to the Neuroflow platform. In both recruitment methods, participants will be required to sign up for a 15 minute check in and check out meeting before and after the trial to answer participant questions regarding the app/app set up or concerns about the consent form. Furthermore, a Qualtrics survey will also be dispersed to participants to be taken during this time along with an initial baseline assessment (to be administered in the NeuroFlow app). Baseline and post-app usage Qualtrics survey links will also be sent with measures

(Generalized anxiety disorder (GAD), Patient Health Questionnaire (PHQ), World Health Organization-Five Well-Being Index (WHO-5), and Difficulties in Emotion Regulation Scale (DERS)) to participants in order to assess differences in user retention. In both conditions, participants will use the Neuroflow app throughout the duration of the 4-week study (28 days). Participants will be sent a push notification each day through the app to complete their daily activities, which could include surveys, videos, or skill-based practice materials. With the collaboration of the Neuroflow team, the usage metrics of the app will be pulled after the end of the study. The user metrics of interest are identifying factors that include first name, last name, gender, age, date of birth, and the applicable assignments to each participant - care team manager and behavioral health specialist. Additionally, the first and last score, first and last date, and time between the first and last assessment dates for the measures of interest (PHQ-9, GAD-7, WHO-5, DERS). Furthermore, the total activity number and the total activity rate across all measures will be collected. No additional data from or about participant phone usage or activities will be pulled as part of the study other than the usage metrics specified above, specific to Neuroflow.

## The following documents are currently attached to this item:

There are no documents attached for this item.

#### **Deception**

Does your project use deception? Deception could be considered any direct misinformation presented to the subject or omission of key information pertaining to the design or nature of the project.

No

#### **International Research**

Are you conducting research outside of the United States?

### **Analysis Plan**

The anticipated statistical analyses to be conducted for this study is a Linear-mixed effects model (LMMs). These models will be used to examine the effect of different incentives (behavioral economics and financial vs. behavioral economics only) on user engagement (measured by the number of active users, the number of activities completed, and completion of daily mood and sleep ratings) and retention. We will also examine the effect of incentive type on secondary mental health outcomes such as anxiety symptoms (GAD-7total score), depression symptoms (PHQ-9 total score), wellbeing (WHO-5total score)and emotion regulation (DERS total score).

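### The itemised app-data pull does not supply rating completion or app retention, both primary, and retention has no event or time window

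*Combined protocol and SAP*

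**What the plan says.** Overall objectives and the Analysis Plan name the same primary measures: engagement, "measured by the number of active users, the number of activities completed, and completion of daily mood and sleep ratings) and retention". The model is given in one sentence: "The anticipated statistical analyses to be conducted for this study is a Linear-mixed effects model (LMMs".

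The Procedures section first describes engagement through "utilization data (ie., daily, weekly, and monthly active users", together with "measures of the total number of activity counts completed by a user". Later in the same section it itemises what will be obtained from the app company after the study ends:

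- identifiers and care-team assignments;
- for PHQ-9, GAD-7, WHO-5 and DERS, "the first and last score, first and last date, and time between the first and last assessment dates for the measures of interest";
- "the total activity number and the total activity rate across all measures will be collected".

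It then closes the list: no further usage or activity data "will be pulled as part of the study other than the usage metrics specified above, specific to Neuroflow".

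On retention, the Procedures section says that the symptom questionnaires are sent "to participants in order to assess differences in user retention". The Design section instead speaks of retention on the NeuroFlow platform itself. No section gives an event, a time point or an inactivity rule.

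**The concern.** The outcomes and the data list were evidently written separately. The list carries one activity total per person and no dates of app use. Its only dates are those of questionnaire assessments. It has no field for mood or sleep ratings, although the daily check-in is what participants are asked to do for 28 days.

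At stake is half of the primary question. The trial asks whether gift cards keep students using the app and completing daily ratings. If the list is followed literally, the only full engagement comparison is of total activities, and a total mixes how long people stay with how much they do while they are there. The pull is a single extraction after the study and its contents are restricted, so the gap should be closed before then.

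**Working it through.** The documents state no power, effect size, drop-off or activity rate on this point, so there is no planned figure to reproduce. The check has three steps.

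**1. Outcomes against the itemised list**

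| Measure | Named in | Available from the itemised list? |
|---|---|---|
| Activities completed | Objectives, Procedures, Analysis Plan | Yes (total per person) |
| Monthly active users | Procedures | Yes, if defined as a total above 0 |
| Daily active users | Procedures | Not itemised |
| Weekly active users | Procedures | Not itemised |
| Mood-rating completion | Objectives, Analysis Plan | No |
| Sleep-rating completion | Objectives, Analysis Plan | No |
| App retention | Objectives, Design, Procedures, Analysis Plan | No (dates are questionnaire dates) |

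Of the six engagement items, two are supplied. Retention is not.

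**2. A constructed example**

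Take two arms of 50 (100 enrolled; the equal split is assumed), with 28 activities per person in both.

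- Arm A, one activity a day: mean daily active users 50; weekly 50, 50, 50, 50; active on day 28: 50.
- Arm B, four a day in week 1 and then nothing (4 × 7 = 28): mean daily active users 50 × 7/28 = 12.5; weekly 50, 0, 0, 0; active on day 28: 0.

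The listed total is 28 per person in both arms, and monthly active users are 50 in both. The list cannot tell complete retention from none.

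**3. A less extreme example**

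All rates here are assumed. A participant drops out of use with constant probability h per day, is active on 80% of days while still a user, and does 1.5 activities per active day.

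- Expected days as a user over 28 days: (1 − (1 − h)^28) / h.
- Retention, meaning any activity in days 22-28: (1 − h)^21 × (1 − e). Here e is the chance that someone still a user on day 22 shows no activity in the window: e = Σ(j = 1 to 6) h(1 − h)^(j−1) × 0.2^j + (1 − h)^6 × 0.2^7.

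For h = 0.04:
- days as a user = (1 − 0.96^28)/0.04 = 17.03;
- retention = 0.4243 × (1 − 0.0099) = 0.420;
- mean total = 17.03 × 0.8 × 1.5 = 20.4.

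For h = 0.02:
- days as a user = (1 − 0.98^28)/0.02 = 21.60;
- retention = 0.6543 × (1 − 0.0050) = 0.651;
- mean total = 21.60 × 0.8 × 1.5 = 25.9.

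The ratio of totals is 21.60/17.03 = 1.27, and the retention difference is 0.651 − 0.420 = 0.231, or 23 points.

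Now hold h at 0.04 in both arms and raise activities per active day in one arm from 1.5 to 1.5 × 1.27 = 1.90. The ratio of totals is again 1.27, and the retention difference is 0.

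| Daily drop-off, halved | Ratio of totals | Retention difference if drop-off is the cause | If more is done per active day |
|---|---|---|---|
| 4% to 2% | 1.27 | 23 points | 0 |
| 3% to 1.5% | 1.20 | 20 points | 0 |
| 2% to 1% | 1.14 | 16 points | 0 |

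**The case against.** **The limit may be wider than it looks.** The closing sentence refers to metrics specified above, and the same Procedures section earlier names daily, weekly and monthly active users. Subject Confidentiality also mentions, in general terms, data on how participants use the platform. On that reading active users fall within the pull. This stands: a reader might infer that active users cannot be obtained at all, and the documents do not support that. What remains is that the itemised list omits them, and that mood and sleep rating completion is absent on either reading.

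**Retention is not really ambiguous.** A reader might infer from the questionnaire sentence that retention means returning the post-study survey. The Design section places retention on the app, Study duration says the surveys serve changes in mental health outcomes, and the Analysis Plan treats the scales that way. The questionnaire phrase is best read as a drafting slip. This also stands, but an operational rule is still missing.

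**The model is not at fault.** It is tempting to argue that a linear mixed model without a stated unit is an error, or that counting active users by arm with days as replicates would inflate false positives. The documents do not support either. Subjects are randomised individually in a between-subjects design, activities are counted per user, and no head-count test is planned. With daily data and a participant random intercept the named model is sound. With one total per person it reduces to ordinary regression. The unstated unit is missing detail, and the choice between linear and logistic models is one of scale.

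**This is an exempt pilot with analyses described as anticipated.** That lowers the detail one should expect, but it does not make an unlisted primary outcome computable.

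**Conclusion.** The concern holds as a mismatch between the primary outcomes and the itemised data, and it should be fixed. Followed as itemised, the pull supports a comparison of activity totals and an ever-active count, but not rating completion or app retention. Daily and weekly active users depend on a generous reading of one sentence. Retention needs an event and a window.

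The mapping rests on the text alone. The size rests on assumed rates: constant daily drop-off, 80% daily activity and 1.5 activities per active day. Across starting drop-off of 2% to 4% per day, the same ratio of totals (1.14 to 1.27) fits a retention difference of 16 to 23 points or of none. These figures show what a total hides. They do not predict this trial's result, and no inflated error rate is attributed to the planned model.

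**What to change.** 1. **Data list (Procedures).** Before the pull, reconcile the list with Overall objectives, the opening of Procedures and the Analysis Plan. Add, per participant and per study day (days 1-28): app activity (yes/no and count), mood-rating completion and sleep-rating completion. Check that the limiting sentence and the consent wording allow these fields; the consent form was not available here.

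2. **If only summaries can be exported.** Request number of active days, number of mood ratings, number of sleep ratings and last active date, all restricted to each participant's own days 1-28. Without that restriction, a last active date after day 28 could be counted as retention when there was no activity in the window. Daily and weekly active users are then unavailable.

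3. **Retention.** Define it per participant as app activity in a stated late window, for example any activity in days 22-28. Report return of the post-study survey separately, and correct the phrase that ties the questionnaires to retention.

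4. **Analysis Plan.** State that arms are compared with the participant as the unit, using either participant-level values or the planned mixed model with a participant random intercept on daily data. Report head counts of active users by arm descriptively.

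The cost is a data-list amendment, a few sentences of wording, a check against the consent form and a somewhat larger export from the app company. No extra participants or visits are needed.

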# **Protocol**

# **Objectives**

#### Overall objectives

Primary: Differences in user engagement and retention over four weeks (28 days) by two forms of behavior economics incentives (either with its usual system of point incentives or with financial incentives). User engagement will be measured by the number of active users, the number of activities completed, and completion of daily mood and sleep ratings. Secondary: Differences in user anxiety, depression, well-being and emotion regulation levels after engagement with the NeuroFlow app, and how it varies by the incentives used for app engagement.

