# Study Design

### Design

This is a two-arm randomized controlled trial assessing the impact of various incentives (points or monetary) on user engagement and retention on the mobile mental health platform, Neuroflow. This study will utilize a block randomization procedure to assign subjects to one of two treatment groups and a between-subjects design in order to understand how the different incentives impact user engagement with the platform. After consenting to participate in the study, participants will be asked to complete the NeuroFlow daily check in for 28 consecutive days, incentivized by either points only, or points redeemable for gift cards (monetary incentive).

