#### **Study duration**

Participants will be actively in the study for approximately one month including four weeks (28 days) of app usage, with time to fill out the pre and post Qualtrics survey to examine changes in mental health related outcomes. Overall, participant recruitment for the study will span the Fall 2021 and Spring 2022 semesters.

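### The plan gives the collected baseline score no role in the mental-health comparison; stating a baseline-adjusted contrast would gain precision at no cost in data

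*Combined protocol and SAP*

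**What the plan says.** The Analysis Plan section is the only statement of statistical method, and nothing is attached to it. It anticipates linear mixed-effects models. For the secondary outcomes it says: "We will also examine the effect of incentive type on secondary mental health outcomes such as anxiety symptoms", then lists the GAD-7, PHQ-9, WHO-5 and DERS totals. It gives no fixed effects, time term, arm-by-time term or covariate, and no role for the baseline score.

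Two other sections describe the target, and they differ:

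- Overall objectives: "Differences in user anxiety, depression, well-being and emotion regulation levels after engagement with the NeuroFlow app". This reads as a comparison of scores after app use.
- Study duration: "pre and post Qualtrics survey to examine changes in mental health related outcomes". This reads as a comparison of change.

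The baseline scores will exist. Procedures says: "Baseline and post-app usage Qualtrics survey links will also be sent with measures", and names all four scales. The same section plans an extract from the app of "the first and last score, first and last date, and time between the first and last assessment dates for the measures of interest".

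**The concern.** With one score before and one after app use, the arms can be compared on the post score, on the change, or on the post score adjusted for baseline. The three target the same treatment effect in a randomized trial but differ in precision. The two that the text suggests are the two less efficient ones.

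Naming a mixed model does not settle the matter. A two-visit mixed model can reproduce either the change analysis or the adjusted analysis, depending on whether each arm has its own baseline mean.

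What is at stake is the precision of the secondary aim, which asks whether financial incentives have a knock-on effect on mental health, in a trial of 100 people. A change contrast also carries any chance baseline imbalance into the realized estimate through regression to the mean. Leaving the form open further allows it to be chosen after results are seen, on four scales.

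**Working it through.** **Inputs from the documents.** 100 participants (Subjects enrolled by Penn Researchers). Two arms: "This study will utilize a block randomization procedure to assign subjects to one of two treatment groups" (Design). One pre and one post survey around 28 days of app use (Study duration).

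**Assumed, because the documents do not give them.** 1:1 allocation, so n = 50 per arm. The same SD σ at both visits. Complete pairs of scores. Two-sided 5% level and 80% power. Baseline-to-post correlation r from 0.4 to 0.8.

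The plan states no power, SD or detectable difference, so there is no figure of its own to reproduce.

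**Variance of the arm difference**, written as (2σ²/n)·v:

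- post score: v = 1
- change score: v = 2(1−r)
- baseline-adjusted: v = 1−r²

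Saving against change = 1 − (1−r²)/[2(1−r)] = 1 − (1+r)/2 = (1−r)/2. Saving against post = r².

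Detectable difference in SD units = (1.960 + 0.842)·√(2v/50).

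| r | v, change | v, adjusted | Saving vs change | Saving vs post | Detectable: post | change | adjusted |
|---|---|---|---|---|---|---|---|
| 0.4 | 1.20 | 0.84 | 30% | 16% | 0.560 | 0.614 | 0.514 |
| 0.5 | 1.00 | 0.75 | 25% | 25% | 0.560 | 0.560 | 0.485 |
| 0.6 | 0.80 | 0.64 | 20% | 36% | 0.560 | 0.501 | 0.448 |
| 0.7 | 0.60 | 0.51 | 15% | 49% | 0.560 | 0.434 | 0.400 |
| 0.8 | 0.40 | 0.36 | 10% | 64% | 0.560 | 0.354 | 0.336 |

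At r = 0.5: 2.802 × √0.04 = 0.560 for post or change, and 2.802 × √0.03 = 0.485 adjusted. An unadjusted analysis would need 50/0.75 ≈ 67 per arm to match.

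**Does naming a mixed model decide it?** Generalized least squares variances with 50 per arm, r = 0.6 and σ = 1:

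- arm, time and arm-by-time, with free baseline means: 0.0320 = 2 × 0.80/50, the same as change
- both visits with one common baseline mean: 0.0256 = 2 × 0.64/50, the same as covariate adjustment
- post score only: 0.0400 = 2/50

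The Analysis Plan wording covers all three. The best has 1 − 0.0256/0.0400 = 36% less variance than the worst.

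**Sensitivity to dropout.** With 40 complete pairs per arm and r = 0.5, the detectable difference goes from 0.626 to 0.543 SD. The proportional variance saving is unchanged.

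**The case against.** The strongest reply is that the plan is silent, and silence is not a decision. A reader might infer that the trial has chosen not to adjust for baseline. The documents do not support that: the mixed model is only anticipated, adjustment is neither stated nor excluded, and one admissible form of the model loses nothing. This stands, and it is why the point is about stating the efficient contrast rather than reversing a choice.

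Several further objections stand in part:

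- The percentages depend on an r that the documents do not give, and on equal SDs at both visits. They are therefore shown as a range.
- Fifty complete pairs per arm is optimistic. Retention is itself a primary outcome, and Potential Study Risks makes every question optional. This worsens the absolute figures but not the proportional savings.
- These are secondary outcomes in a self-described pilot with no stated precision target. That limits the weight of the point, but the comparison is a declared aim and the data are already planned.
- The baseline itself needs defining. Procedures describes both a Qualtrics survey and an in-app baseline assessment, and places random assignment after consent without saying whether baseline is completed before the participant knows the arm. Adjustment is sound only for a baseline that the assignment cannot have influenced, so the fix has to cover this.

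**Conclusion.** The point holds as a free gain in precision. The Analysis Plan gives the collected baseline score no role, and the contrasts suggested elsewhere, post levels or changes, are both less precise than a baseline-adjusted one. Under the assumptions listed (r of 0.4 to 0.8, equal SDs, complete data, 50 per arm), the variance saving is 30% down to 10% against change scores and 16% up to 64% against post scores.

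Two stronger readings do not follow. First, a reader might infer that the loss is always larger for a post-score analysis. That is true only for r above 0.5: the savings are equal at 0.5, and at 0.4 they are 16% against post and 30% against change. Second, a reader might infer that an unadjusted comparison would be biased. Under randomization it would not be. Baseline imbalance here is a matter of chance in the realized trial, and regression to the mean enters only if a change contrast is used, which the Analysis Plan does not say.

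**What to change.** Add to the Analysis Plan that, for each of the GAD-7, PHQ-9, WHO-5 and DERS totals, the arm difference at the post survey is estimated in one of two ways, chosen in advance:

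1. with that scale's pre-app Qualtrics score as a covariate; or
2. with a two-visit mixed model that constrains the arms to a common baseline mean.

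With complete data the two give the same variance in the calculation above. The second also keeps participants who have only one of the two scores, and it stays within the mixed-model framework already planned. Report the adjusted difference with a 95% CI as the secondary result.

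Name the Qualtrics score as the baseline, rather than the in-app first score, and state that it is completed before the participant learns the arm. Align Overall objectives and Study duration with the chosen contrast.

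The cost is a few sentences. It needs no new data and adds no participant burden. If the current order of steps does not already place the baseline survey before the arm is known, that order would also have to be set.

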# Risk / Benefit

### **Potential Study Risks**

We anticipate very few risks associated with participating in the study. Participants may feel uncomfortable answering certain questions, but all questions will be optional and there will be no penalties or consequences associated with choosing to opt out of providing certain information. As with any study taking personal information, there is the risk of a possible data breach that could expose information about participants mental health, However, we will be deidentifying our dataset and any datasets with identifying information will be password locked. Only study personnel will have access to any data associated with the study. In the event of a mental health crisis or reports of suicidal ideation, the NeuroFlow platform lists emergency resources within the app.

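### Post-study mental-health scores may be missing more often in participants who disengage, and a mixed model without engagement can then bias the secondary arm comparison

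*Combined protocol and SAP*

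**What the plan says.** The Analysis Plan names a linear mixed model for all outcomes. For the scales it says "We will also examine the effect of incentive type on secondary mental health outcomes such as anxiety symptoms", then lists total scores on GAD-7, PHQ-9, WHO-5 and DERS. Incentive type is the only predictor named. Nothing is said about missing scores, the analysis set, baseline adjustment or sensitivity analysis.

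The primary objective is "Differences in user engagement and retention over four weeks (28 days) by two forms of behavior economics incentives". The Background asks whether the financial incentive raises engagement or has downstream effects on mental health.

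The post scores have two described sources:

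- **Qualtrics.** Procedures states "Baseline and post-app usage Qualtrics survey links will also be sent with measures", listing the four scales, and "participants will be required to sign up for a 15 minute check in and check out meeting before and after the trial". Neither is described as conditional on app use.
- **The app.** Procedures also has the vendor supply "the first and last score, first and last date, and time between the first and last assessment dates" for the same scales along with the usage metrics. Subject Confidentiality likewise describes the post-use assessment as collected through the app.

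The plan does not say which source feeds the analysis. Potential Study Risks adds that "all questions will be optional", and the Consent section allows withdrawal at any time.

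**The concern.** A likelihood-based mixed model gives a valid arm comparison when missingness is at random given what is in the model. Suppose the model holds arm, time and baseline score, which is already more than the plan states. If the chance of a post score also depends on engagement during the 28 days, and engagement is related to the post score, that condition fails.

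This trial is more exposed than most because engagement is the variable the arms are designed to move. Responders in the two arms may then resemble each other in engagement more than the randomised groups do. Under the app route the risk is direct: someone who stops early has no later score, or an early one standing in for day 28. A null or positive secondary result could not then be separated from selective response.

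**Working it through.** **No plan figure to reproduce.** Planned enrolment is 100, without derivation. No alpha, power, effect size, SD or dropout rate is given. Everything below uses assumed inputs.

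**Set-up** (1,000,000 simulated participants per scenario, 1:1 allocation assumed). Z = 1 for the gift-card arm, B = baseline score, E = engagement in SD units, U = an unmeasured factor.

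- E = 0.5·Z + noise with SD 1 (shift 0 in row 8). In rows 4–7, U has loading 0.6 in E.
- Y = 0.6·B − b·E − d·Z − s·U + 0.7·error. Lower is better, and Y is approximately in SD units.
- P(post score observed) = 1 / (1 + exp(−(a + c·E))), with a = 0.8 and c = 1.5 except in rows 2 (a = 1.2, c = 0.8) and 3 (a = 1.0, c = 0).

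Four estimates of the arm difference were compared: full data; observed data adjusted for baseline; the same with E as a covariate; and regression imputation from arm, baseline and E followed by an arm comparison without E.

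| Row and mechanism | Full data | Without E | E as covariate | E as auxiliary |
|---|---|---|---|---|
| 1. Benefit only through engagement (b = 0.4); missing 36% v 25% | −0.200 | −0.153 | 0.003 | −0.197 |
| 2. Same, weaker link; missing 26% v 20% | −0.200 | −0.182 | 0.001 | −0.199 |
| 3. Missingness unrelated to engagement; 27% in both | −0.199 | −0.201 | 0.001 | −0.200 |
| 4. No effect; engaged people do better (s = 0.5) | −0.003 | +0.030 | +0.145 | −0.003 |
| 5. No effect; people who recover leave (s = −0.5) | 0.001 | −0.033 | −0.149 | 0.002 |
| 6. Benefit as row 1, and recoverers leave (s = −0.7) | −0.200 | −0.202 | −0.210 | −0.199 |
| 7. b = 0.2, d = 0.1, recoverers leave (s = −0.7) | −0.198 | −0.221 | −0.306 | −0.197 |
| 8. Incentive does not move engagement; b = 0.4, d = 0.2 | −0.201 | −0.198 | −0.198 | −0.199 |

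**Attenuation.** Row 1: 1 − 0.153/0.200 = 24%. Row 2: 1 − 0.182/0.200 = 9%. A fitted two-time-point mixed model under row 1 (20,000 participants) gave −0.130, SE 0.013, or 1 − 0.130/0.200 = 35%. Its 95% range, −0.130 ± 1.96 × 0.013 = −0.155 to −0.105, includes −0.153, so 24% is the steadier figure.

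**Why the sign varies.** In row 1 the responders' engagement gap is 0.153/0.4 = 0.38, not 0.50, so selection removes about 0.12. The bias is about −0.12 times the overall slope of Y on E, which is −b − 0.6·s where U is present.

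- Row 4: slope −0.30, predicted +0.036; simulated 0.030 − (−0.003) = +0.033.
- Row 5: slope +0.30, predicted −0.036; simulated −0.033 − 0.001 = −0.034.
- Row 6: slope −0.4 + 0.42 = +0.02, predicted −0.002; simulated −0.202 − (−0.200) = −0.002.
- Row 7: slope −0.2 + 0.42 = +0.22, predicted −0.026; simulated −0.221 − (−0.198) = −0.023.

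**Size against noise at N = 100.** In row 1 the observed numbers are 50 × 0.638 = 31.9 and 50 × 0.753 = 37.7. Residual SD given baseline is √(0.4² + 0.7²) = 0.81. SE = 0.81 × √(1/31.9 + 1/37.7) = 0.19. The bias is 0.200 − 0.153 = 0.047, about a quarter of one SE. At an assumed two-sided 0.05 and 80% power, the detectable difference is 2.80 × √(2/50) = 0.56 SD with 50 per arm and 2.80 × √(2/35) = 0.67 SD with 35. A rerun at N = 100 gave a sampling SD of about 0.20 with or without engagement-based imputation, so precision was essentially unchanged.

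**The case against.** A reader might infer that the scales are in fact missing for people who disengage. The documents do not support that. The Qualtrics links and the check-out meeting stand outside the app, and participants recruited through SONA receive 4 credits after completing the study, with no mention of arm. Someone can abandon the app and still complete the survey. This stands: engagement-driven missingness is a risk. The risk remains because the app-based source is also described, questions are optional, withdrawal is free, and no completion credit is described for participants recruited by other routes.

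A reader might also infer that the planned model must shrink the arm difference. That holds only when greater engagement goes with better scores. The documents do not say why people leave, and rows 3 to 8 show no material bias, a false difference in either direction, or inflation.

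The size is open to challenge too. Every parameter is assumed, the bias is small against sampling error, and these are secondary outcomes of a pilot. The near-exact recovery by imputation follows from the set-up, in which missingness depended only on measured engagement; it would not hold if missingness also depended on the unseen score. All of this stands and limits the weight of the point. It does not remove the case for a prespecified method, because the method is cheap and the direction of bias could not be judged afterwards.

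**Conclusion.** The concern holds as a risk of bias of uncertain direction. If response depends on engagement and engagement relates to the post score, a mixed model with only arm, time and baseline score can misstate the secondary arm difference. Bias is towards no difference if benefit runs through engagement, the pathway the Background raises. Under assumed inputs the attenuation was roughly 10–35%, about 0.02 to 0.07 SD on a true 0.20 SD, against an SE of about 0.2 SD at N = 100. The documents cannot confirm any of these sizes.

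The remedy must not be read as adding engagement to the outcome model. It is post-randomisation and on the suspected causal path; as a covariate it erased the whole effect in row 1 (0.003) and created differences of +0.145 and −0.149 where none existed in rows 4 and 5.

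**What to change.** Amend the Analysis Plan and Procedures as follows.

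1. Name the post-study Qualtrics score as the source for the four scales, and seek it from everyone randomised whatever their app use.
2. Report missing post scores by arm and by level of engagement.
3. Analyse all randomised participants, imputing missing post scores from arm, baseline score and engagement measures already collected: total activity number and rate, and daily active use or check-in completion. The last day of use is not among the listed metrics, so the method should not depend on it.
4. Keep engagement out of the arm-comparison model.
5. Add one delta-shift sensitivity analysis for missingness that depends on the unseen score.

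The cost is some plan text and modest analyst time. No new instrument or participants are needed. With about 50 per arm, the imputation model must be kept small.
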